4.4. End of Study Definition

The end of the study is defined as the date of the last visit of the last participant in the study or last scheduled procedure shown in the SoA (Section 1.3) for the last participant in the study.

The Exit visit is defined as the last visit or the last scheduled procedure shown in the SoA for each stage of the study (Section 1.3). A participant is considered to have completed the study if he/she has completed all study visits including the Exit visit. If the participant is discontinued or withdraws from the study before the Exit visit, the last visit before the discontinuation or withdrawal will be considered an Early Termination visit.

5. Study Population

All participants will have DED. In addition, participants enrolled in Stage 2 of this study will have to respond to the CAE challenge with increased signs and symptoms of DED (see Sections 4.1 and 4.2.4 for more details).

Prospective approval of protocol deviations to recruitment and enrollment criteria, also known as protocol waivers or exemptions, is not permitted.

5.1. Stage 1

5.1.1. Inclusion Criteria for Stage 1

Participants are eligible to be included in Stage 1 of the study only if all of the following criteria apply:

1.	Age
1.01	Participant must be ≥ 18 years of age at the time of signing the informed consent
2.	Type of Participant and Disease Characteristics
2.01	Both of the following signs of DED in at least 1 eye at Screening and Baseline visits (the same eye does not need to qualify at both visits):
	 Total corneal fluorescein staining score ≥ 2 and ≤ 9 based on the NEI grading scale, with no score > 2 in any 1 region
	• Schirmer test with topical anesthesia score ≥ 1 and ≤ 10 mm/5 min
2.02	Symptoms of DED at both the Screening and Baseline visits as defined by an OSDI total score of ≥ 13 with ≤ 3 responses of "not applicable (NA)".
2.03	BCVA of 20/100 or better in both eyes at the Screening visit
2.04	Good general and ocular health, as determined by the investigator using medical history, ophthalmic examination and history, physical examination, fasting blood chemistry and hematology, urinalysis, vital signs, and 12-lead ECG results at the Screening and Baseline visits, as applicable per the SoA (Section 1.3).
3.	Sex
3.01	Male or female

4.	Contraceptives	
4.01	Male participants willing to minimize the risk of inducing pregnancy for the duration of the clinical study	

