7.1. Discontinuation of Study Intervention

Participants who discontinue the study intervention early will be encouraged to return for the Early Termination visit assessments. See the SoA (Section 1.3) for data to be collected at the time of intervention discontinuation and follow-up, and for any further evaluations that need to be completed.

Discontinuation of study intervention for abnormal liver function must be considered by the investigator when a participant meets the potential Hy's Law criteria outlined in the adverse events of special interest (AESI) section (Appendix 3) or if the investigator believes that it is in best interest of the participant.

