7.2. Participant Discontinuation/Withdrawal from the Study

- A participant may withdraw from the study at any time at his/her own request or may be withdrawn at any time at the discretion of the investigator for safety, behavioral, compliance, or administrative reasons.
- Participants may be discontinued at the discretion of the investigator and/or the sponsor if they use any prohibited treatments described in Section 6.5.4.
- For participants who discontinue from the study early, every effort must be made to have these participants return to the clinical center for completion of the Early Termination visit. AEs leading to participant early discontinuation must be followed-up as appropriate.
- If the participant withdraws consent for disclosure of future information, the sponsor may retain and continue to use any data collected before such a withdrawal of consent.
- See the SoA (Section 1.3) for data to be collected at the time of study discontinuation (Early Termination). If the Early Termination visit falls on the same day as another scheduled visit, only Early Termination visit assessments will be conducted.
- Study termination

The dosing of study intervention may be paused due to safety concerns at any time by the site investigator. The sponsor and DMC must be notified immediately if the dosing was paused.

The sponsor may stop the study (and/or the study site) for any reason with appropriate notification.

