8.2.1. Time Period and Frequency for Collecting AE and SAE Information

All AEs and SAEs from the signing of the ICF until the Exit visit or Early Termination visit will be collected at the timepoints specified in the SoA (Section 1.3), and as observed or reported spontaneously by study participants.

Medical occurrences that begin before the start of study intervention, but after obtaining informed consent will be recorded in the AE section of the eCRF and will be considered pretreatment AEs.

All SAEs will be recorded and reported to the sponsor or designee within 24 hours, as indicated in Appendix 3. The investigator will submit any updated SAE data to the sponsor within 24 hours of it being available.

Investigators are not obligated to actively seek AE or SAE information after conclusion of the study participation. However, if the investigator learns of any SAE, including a death, at any time after a participant has been discharged from the study, and he/she considers the event to be reasonably related to the study intervention or study participation, the investigator must promptly notify the sponsor.

The method of recording, evaluating, and assessing causality of AEs and SAEs and the procedures for completing and transmitting SAE reports are provided in Appendix 3.

[figure not shown]

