9.4.2.1. Adverse Events

For each stage, the Medical Dictionary for Regulatory Activities (MedDRA) nomenclature will be used to code AEs.

An AE will be considered a treatment-emergent AE (TEAE) if either of the following apply:

- The AE began on or after the first dose of study intervention.
- The AE was present before the date of the first dose of study intervention but increased in intensity or became serious on or after the date of the first dose of study intervention.

An AE will be considered a treatment-emergent SAE (TESAE) if it is a TEAE that additionally meets any SAE criteria.

An AE that occurs after the Exit or Early Termination visit will not be counted as a TEAE.

The number and percentage of participants reporting TEAEs in each study intervention group will be tabulated by:

- 1) System Organ Class and Preferred Term
- 2) System Organ Class, Preferred Term, and severity

The number and percentage of participants reporting TEAEs and TESAEs will be tabulated separately by study intervention.

If more than 1 AE is coded to the same preferred term for the same participant, the participant will be counted only once for that preferred term using the most severe and most related occurrence for the summarizations by intensity and by relationship to study intervention.

Summary tables will be provided for participants with SAEs regardless of causality and participants with AEs leading to discontinuation.

The definitions of an AE and SAE can be found in Appendix 3.

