9.2.1 Treatment-Emergent Adverse Events

An AE will be considered a treatment-emergent adverse event (TEAE) if the AE began or worsened (increased in severity or became serious) on or after the date of the first dose of study drug. Events where the onset date is the same as the study drug start date are assumed to be treatment emergent.

In general, the number and percentage of participants experiencing TEAEs will be summarized overall, as well as by primary MedDRA SOC and PT. The SOCs will be

presented in alphabetical order, and the PTs will be presented in decreasing frequency order on active study drug within each SOC. The number and percentage of participants experiencing TEAEs will also be summarized by PT for identifying common AEs. TEAEs by PT summaries will be presented in decreasing frequency order on active study drug.

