5.6.2. Adverse Events

An AE will be considered a TEAE if:

- The AE began on or after the first administration of study intervention, or
- The AE was present before the first administration of study intervention, but worsened (increased in severity or became serious) on or after the first dose of study intervention

An AE that occurs after the Exit or Early Termination visits will not be counted as a TEAE.

An AE will be considered a TESAE if it is a TEAE that additionally meets any SAE criterion.

TEAEs will be summarized by cohort and study intervention group using the Safety population.

If more than 1 AE is coded to the same preferred term for the same participant, the participant will be counted only once for that preferred term using the most severe and most related occurrence for the summarizations by severity and by relationship to study intervention.

Listings of all TEAEs, TESAEs, TEAEs leading to discontinuation by participant, and deaths will be presented.

AEs will be coded using MedDRA version 23.0 or newer. Unique participants reporting AEs in the following AE categories will be summarized by cohort and study intervention group for the Safety Population as follows:

Safety Statistical Analysis Plan

2012-201-005 [Stage 1]

Table 5-4 TEAE Summaries

Parameters	Description	Methodology
AE	Overall summary by cohort and study intervention group only for the following categories: TEAEs Treatment-related TEAEs TESAEs Treatment-related TESAEs TEAEs leading to study discontinuation Deaths	Categorical descriptives
TEAEs	Overall summary by cohort and study intervention group and by SOC and PT Participants categorized overall and within each SOC and PT in decreasing frequency	Categorical descriptives
TEAEs by severity	Overall summary by cohort and study intervention group and by SOC, PT, and severity • Participants categorized overall and within each SOC and PT in decreasing frequency for the most severe occurrence	Categorical descriptives
Treatment-related TEAEs	Overall summary by cohort and study intervention group and by SOC and PT • Participants categorized overall and within each SOC and PT in decreasing frequency	Categorical descriptives
TESAEs	Overall summary by cohort and study intervention group and by SOC and PT ^a	Categorical descriptives ¹ Supportive data listing
TEAEs leading to discontinuation	Overall summary by cohort and study intervention group and by SOC and PT ^a	Categorical descriptives ¹ Supportive data listing

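### Protocol 4.4 conflicts with 7.1, 7.2 and the SoA on what the Early Termination visit is; read literally, it puts on-treatment AEs of participants who never return outside AE collection and outside the Stage 1 TEAE tables

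*Protocol*

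**What the plan says.** **What the ET visit is.** Protocol Section 4.4 states that, when a participant is discontinued or withdraws before the Exit visit, "the last visit before the discontinuation or withdrawal will be considered an Early Termination visit". Section 7.1 describes something else: "Participants who discontinue the study intervention early will be encouraged to return for the Early Termination visit assessments". So does Section 7.2, under which "every effort must be made to have these participants return to the clinical center for completion of the Early Termination visit". Section 7.2 also covers an ET visit that coincides with a scheduled visit. The Schedule of Activities gives ET its own instructions, such as a single PK blood sample.

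**What hangs on it.** Section 8.2.1 sets the collection window: "All AEs and SAEs from the signing of the ICF until the Exit visit or Early Termination visit will be collected". Section 9.4.2.1 sets the analysis cut-off: "An AE that occurs after the Exit or Early Termination visit will not be counted as a TEAE". The Stage 1 SAP, Section 5.6.2, repeats it: "An AE that occurs after the Exit or Early Termination visits will not be counted as a TEAE".

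**Stage 2 differs.** The Stage 2 SAP, Section 9.2.1, counts an AE as treatment-emergent "if the AE began or worsened (increased in severity or became serious) on or after the date of the first dose of study drug" and gives no end point. Its Appendix E, on changes to protocol-planned analyses, mentions only that the between-group safety comparisons were dropped.

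**The concern.** Safety and tolerability are the primary objective in Stage 2 and a primary objective in Stage 1, so the date that closes the AE window is one of the most consequential definitions in the plan. Two incompatible definitions of that date are in force. Under one of them, the window closes at a visit made before the participant decided to leave. An AE that began after that visit, while the participant was still dosing, then lies outside the window even if it is the reason for leaving. Such a loss is selective by construction: it can affect only people who stopped early. It could also leave a Stage 1 participant counted in the disposition table as discontinued for an AE, with no matching event in the TEAE tables.

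**Working it through.** The documents give no figure to reproduce here: the sample size is described as empirical, and no AE, withdrawal or non-return rate is assumed. The check is therefore of the wording first, then of the weight of a single event.

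**Step 1. Follow one Stage 1 participant.** Suppose the participant attends Visit 4 (Day 8), has an AE afterwards while still dosing, and leaves before Visit 5 (Day 15).

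| | ET visit by 4.4, read literally | ET visit by 7.1, 7.2 and the SoA |
|---|---|---|
| Returns after the AE | Visit 4 if withdrawal is dated before the return; the return visit if withdrawal is dated from it | The return visit. The AE precedes it, so it is collected and is a TEAE |
| Never returns | Visit 4. The AE follows it, so it is outside collection and is not a TEAE | No ET visit takes place, and the cut-off has no date |

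For the returning participant the outcome depends on which section the site follows. For the one who never returns, 4.4 is the only section that supplies an ET date, and that date excludes the event. Section 7.3 foresees such participants.

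**Step 2. Which outputs are exposed.**
- *Collection, both stages.* The Section 8.2.1 window ends at Exit or ET whatever either SAP says. Capture of new concomitant medication (Section 6.5.2) and the potential Hy's Law reporting requirement (Appendix 3) end at the same visit.
- *Stage 1 tables.* Stage 1 SAP 5.6.2 and Table 5-4 build the overall, severity, relatedness, serious-event and discontinuation summaries on TEAEs. The discontinuation listing is also TEAE-based, and the discontinuation table is made only if at least 5 participants are affected.
- *Stage 2 tables.* The TEAE definition has no end date, so a recorded event is kept. The table and listing of AEs leading to study drug discontinuation (Stage 2 SAP 9.2.4) are not worded as limited to TEAEs.

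**Step 3. Treatment days between visits, on nominal days.**
- Stage 1, visits on Days 1, 2, 8 and 15: gaps of 0, 5 and 6 days, so 0 + 5 + 6 = 11 of 15 days, or 73.3%.
- Stage 2 from Day 1, visits on Days 1, 14, 28 and 42: gaps of 12, 13 and 13 days, so 12 + 13 + 13 = 38 of 42 days, or 90.5%.

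These shares show when an event could fall between visits. They do not show how often one would be lost.

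**Step 4. Weight of one lost participant (100 × 1/n).** Stage 1 tables are by cohort and intervention group, so the per-cohort arm sizes apply.
- Stage 1 active arm, n = 9: 1/9 = 11.1 percentage points.
- Stage 1 vehicle arm, n = 3: 1/3 = 33.3 points.
- Stage 2 arm, n = 50: 1/50 = 2.0 points. For a recorded event this would arise only if the protocol cut-off were applied, and the Stage 2 SAP does not apply it.

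**Step 5. Expected loss.** The expected number per arm is n × P(withdrawal for an AE arising between visits) × P(no return, given such a withdrawal). The documents give neither probability, so this cannot be evaluated.

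**The case against.** The best defence is that 4.4 is loosely worded rather than a working rule. Sections 7.1, 7.2 and the SoA describe a real return visit. If the participant attends it before leaving the study, it is also the last visit before withdrawal, so even 4.4 points to it and the AE is counted. That stands for participants who return. It does not help those who do not, because return is only encouraged or sought.

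A second defence is that such events surface elsewhere. The reason for discontinuation is recorded on the eCRF and summarised by arm in both stages. Section 7.2 requires AEs leading to discontinuation to be followed up. Section 8.2.1 requires investigators to report related SAEs that they learn of after discharge. The Stage 1 SAP promises listings of all data. Protocol 9.4.2.1 also plans a summary of AEs leading to discontinuation that is not restricted to TEAEs. These are real safeguards against an event vanishing without trace. They do not return it to the Stage 1 TEAE tables, nor do they require sites to collect a non-serious AE after the relabelled visit.

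Third, Protocol 9.4.2 leaves the full definition of the safety analysis to the SAP, so the open-ended Stage 2 definition governs the Stage 2 tables. That stands. What remains for Stage 2 is the collection window and the unlisted departure from the protocol.

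**Conclusion.** The point holds as an inconsistency with a specific consequence. Section 4.4 must be reconciled with Sections 7.1 and 7.2 and the SoA. Until then, on the literal 4.4 reading, an on-treatment AE after the last attended visit of a participant who never returns is outside AE collection in both stages. It is also not a TEAE under the protocol or the Stage 1 SAP. In Stage 1 each such participant moves a rate by 11.1 points (active arm) or 33.3 points (vehicle arm), assuming full arms of 9 and 3 and no other event of that kind in the same participant.

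A reader might infer two stronger conclusions, and the documents support neither. One is that these events disappear from the safety tables throughout the trial. The Stage 2 SAP has no ET cut-off, its discontinuation table is not limited to TEAEs, and participants who return can be handled correctly under 7.1 and 7.2. The other is that AE rates are biased downward by a known amount, more so in the less tolerable arm. That direction is plausible, but with no rate of between-visit AE withdrawal or of non-return, neither its size nor any difference between arms can be shown.

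**What to change.** 1. In Protocol 4.4, delete the sentence that relabels the last attended visit, or limit it so that it does not set the AE cut-off.
2. In Protocol 8.2.1 and 9.4.2.1, end AE collection and the TEAE window at the later of the ET visit actually performed or the date of withdrawal or last participation. Stage 1 SAP 5.1 already defines the end of study for a participant as the last date of participation, recorded on the eCRF, so a usable date exists.
3. State the same TEAE definition in the protocol and in Stage 2 SAP 9.2.1, and list the change from the protocol in Appendix E before final lock.
4. Stage 1 was already locked, unmasked and analysed (Stage 2 SAP Section 10.0). Compare AE onset dates with the ET dates used, cross-check participants whose recorded reason for leaving was an AE, and report any on-treatment AE that was excluded as a supplement to the Stage 1 results.

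The cost is wording in the protocol and the Stage 2 SAP, with no new visits, plus a small post-lock check. A few more events may be counted. The Stage 1 check can recover only events that were recorded somewhere.

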5.3. Lifestyle Considerations

5.3.1. Meals and Dietary Restrictions

Participants will be instructed to fast (ie, water only) for at least 10 hours prior to blood collection for safety laboratory tests. Fasting will not be required for the blood PK sample collections. In Stage 2, fasting will not be required.

In Stage 1, participants will be served meals at appropriate times at Visits 3 and 5.

5.3.2. Caffeine, Alcohol, Tobacco, and Cannabis

[figure not shown]
Participants must abstain from drinking alcohol for at least 3 days before each blood collection for safety laboratory tests (Stage 1: Visits 1 and 5 or Early Termination; Stage 2: Visits 1, 3, 5, 6, or Early Termination). This will not be required for the blood PK sample collections.

There are no restrictions on the consumption of caffeine or use of tobacco. However, the participant's current smoking status or use of nicotine-containing products will be assessed at the Screening visit and recorded on the eCRF.

Participants must abstain from using inhalable or ingestible cannabis products or transdermal patches containing THC for at least 30 days before the Screening Visit and throughout the duration of the study.

5.3.3. Activity

Participants must abstain from strenuous exercise for at least 12 hours before each blood collection for safety laboratory tests. This will not be required for the blood PK sample collections.

5.4. Screen Failures

Screen failures are defined as participants who consent to participate in the clinical study but are not subsequently entered in the study. A minimal set of screen failure information is required to ensure transparent reporting of screen failure participants to meet the CONSORT publishing requirements and to respond to queries from regulatory authorities. Minimal information includes indicating screen failure as reason for ending the study, demography, screen failure details, eligibility criteria, and any SAE.

Individuals who do not meet the criteria for participation in this study (screen failures) may be rescreened once. A participant who is rescreened will be screened again in the interactive web response system (IWRS) and given a new participant number.

6. Study Intervention

Study intervention is defined as any investigational intervention, or marketed product intended to be administered to a study participant according to the study protocol.

6.1. Study Intervention(s) Administered

Table 6-1 Study Interventions

Study Intervention Name	AGN-242428	AGN-231868	Xiidra	AGN-242428 vehicle	AGN-231868 vehicle	
Dosage Formulation	Ophthalmic solution	Ophthalmic solution	Ophthalmic solution	Ophthalmic solution	Ophthalmic solution	
Manufacturer	Allergan	Allergan	Shire	Allergan	Allergan	
Concentrations			5%	NA	NA	
Route of Administration	Topical eyedrop	Topical eyedrop	Topical eyedrop	Topical eyedrop	Topical eyedrop	
Dosing Instructions	Participants will be instructed to instill a single drop per eye, twice daily (approximately 12 hours apart) (with the exception of Day 1 in Stage 1 where only the left eye will be dosed once with a single drop and the last day of dosing in both stages where a single dose will be administered to both eyes). On visit days, the morning dose of the intervention will be administered by the site staff. More details on the dosing regimen can be found in Section 6.1.1.					

Packaging and Labeling

In Stage 1, AGN-242428, AGN-231868 and their vehicles will be provided in identical single-use bottles. In Stage 2, AGN-242428, AGN-231868 and their vehicles will be provided in identical single-use vials. Xiidra will be supplied in single-use, commercially available vials that will have the original label overlaid with a new clinical label to prevent unmasking.

All interventions

will be supplied in identical cartons.

All study interventions, including vehicles and marketed products, will be labeled with the protocol number, kit number, warning language (Caution: New Drug—Limited by Federal Law to Investigational Use. Keep Out of Reach of Children), and instructions to take as directed.

Immediately before dispensing the study intervention, the investigator (or appropriately trained designee) will write the participant number, and the date dispensed on the label.

